### **INTRODUCTION AND PURPOSE:**

Despite growing evidence that lung cancer screening (LCS) reduces lung cancer-specific mortality, LCS across the United States and at Penn Medicine is remarkably low. This is due in part to challenges with identifying adults who meet eligibility criteria for lifetime smoking intensity (i.e., 20 pack-years or greater), which is often missing from the electronic medical record. The primary purpose of this nudge study is to test the feasibility and reliability of using three yes/no questions (i.e., the simplified eligibility tool) for predicting pack-year eligibility for LCS. If successful, we intend on using this approach in future trials as a tool to identify LCS-eligible patients and increase LCS.

### **OBJECTIVES:**

The overarching goal of this project is to increase LCS by developing scalable and equitable strategies for identifying screening-eligible patients across Penn Medicine. We seek to achieve this goal through the following interrelated objectives:

- Objective 1. Assess feasibility of using patient-directed outreach to complete the simplified eligibility tool.
- Objective 2: Explore how recruitment messaging content and incentives impact response rates to the survey.

If successful, we intend to use this tool and the results of this study in future intervention trials designed to increase shared decision-making and uptake of LCS. We will also share this tool widely to support equitable LCS uptake across diverse patients and settings. All future trials will be submitted for separate IRB approval.

### **BACKGROUND:**

A growing body of evidence indicates that lung cancer screening (LCS) for high-risk adults reduces lung-cancer mortality by 16-20%. Despite this evidence, uptake of LCS in the United States remains suboptimal (~5% national completion rate in screening-eligible adults). Additionally, there are disparities in uptake by race, sex, and other key social determinants of health, reflective of the challenges of implementing LCS equitably.

LCS differs from other types of population-level cancer screening because eligibility assessment requires evaluation of lifetime smoking intensity, calculated by multiplying the average number of packs of cigarettes smoked per day by total years a person smoked (i.e., pack-years). While tobacco use (i.e., current, former, never) is well captured in electronic medical records (EMR), pack-years is often missing, highlighting the need for interventions focused specifically on this component of LCS-eligibility assessment. Prior approaches to assessing pack-years have used open-ended questions, which in comparison to other question formats (e.g., yes/no) is associated with increased respondent burden and lower response rates. As such, we seek to develop and test the feasibility and reliability of using brief yes/no questions (“simplified eligibility tool”) for predicting 20+ pack-year eligibility for LCS. This approach has shown high positive predictive value (90.5%) in our pilot study with 303 patients, and we are now looking to test the approach in a larger and more diverse sample of adult patients at Penn Medicine. This work will also help to support future pragmatic studies aiming to test strategies to increase lung cancer screening in eligible adults.

### **CHARACTERISTICS OF THE STUDY POPULATION:**

#### ***1. Target Population and Accrual:***

The target population includes primary care patients at Penn Medicine who are potentially eligible for LCS based on age (50-80 years old) or tobacco use (currently smoked or smoked within the last 15 years) but have never been screened for nor diagnosed with lung cancer. Currently, we cannot assess full LCS-eligibility of these patients because most (70% or greater) have no information regarding pack-years in their electronic medical record (EMR); thus, limiting our ability to assess true uptake of LCS in eligible patients and missing an opportunity

to reduce lung cancer mortality in our patients. Given the population health focus, we aim to include all patients who meet study eligibility at Penn Medicine, which we estimate will be approximately 6,125 patients across the study timeline. Patients will accrue as identified in the electronic health record (EHR) throughout the study duration and contacted in batches to monitor enrollment response and address any unintended negative impacts on patients or providers that may arise.

## **2. Key Inclusion Criteria:**

Based on available EMR data, patients will be eligible if they:

- a) meet age eligibility (50-80 years old) for LCS based on 2021 USPSTF guidelines; and
- b) have completed at least one primary care visit at Penn Medicine in 2020-2025

## **3. Key Exclusion Criteria:**

Based on available EHR data, patients will be ineligible if they:

- a) have a documented history of lung cancer;
- b) have a documented history of completing LCS at Penn Medicine;
- c) are listed as not wanting to be contacted or solicited for research; or
- d) do not otherwise meet inclusion criteria.

## **4. Subject Recruitment and Screening:**

We are requesting a waiver of HIPAA authorization to use EHR data to identify potential patient participants who meet study inclusion criteria. To ensure equity in reach, we will use a concurrent and multimodal approach to contacting and recruiting patients. Specifically, all patients with active mobile phones will be contacted first by text message with an invitation to complete the simplified eligibility tool (i.e., yes/no questions included in the protocol) using Way-to-Health. The initial text message will also include an option to “opt-out” of future text messaging or outreach related to the study. Patients who do not respond to text message outreach within one week will be sent a letter delivered via email, patient portal, and/or post (depending on availability of contact information in the EHR or patient portal activation and use). All recruitment materials are included in this application. We will contact patients no more than five times total, regardless of type of outreach (i.e., text, email, post, or portal).

## **5. Early Withdrawal of Subjects:**

Patients can choose not to participate at any time. Participants will be given the option to “opt-out” from future study-related contact via text message or withdraw by contacting the study coordinator (phone and email information included in the recruitment letter).

## **6. Vulnerable Populations:**

Because they are not likely to meet eligibility for LCS, children, pregnant women, fetuses, and neonates are not included in this research study. Prisoners are also not included in this study because they are unlikely to be Penn Medicine patients while incarcerated.

## **7. Populations vulnerable to undue influence or coercion:**

Although we are not specifically targeting Penn Medicine employees, it is possible that a portion of eligible patients will also be employees. However, we will not assess nor share any information related to employer name to avoid undue influence or coercion.

## **STUDY DESIGN:**

We will use a phased, cross-sectional approach to collect patient-reported information related to lifetime smoking history. We will assess correlation between self-reported data with smoking data (i.e., pack-years) in the subset of patients with pack-years documented in their EHR. The overall goal of this study is to develop scalable strategies for increasing identification of patients who meet 20 pack-year eligibility for LCS. The questions used in this study have been pilot tested with a smaller group of 303 patients and shown high positive predictive value (90.5%). We are now seeking to expand upon these results and apply to a larger group of patients to assess population-level reliability and eligibility assessment for LCS (Objective 1). In addition to advancing the development of a screening eligibility tool that can be applied across healthcare systems, we will use the results of the study to identify participants for future intervention trials seeking to improve LCS at Penn Medicine.

The duration of the study will be approximately 2 years, which will give sufficient time to collect patient-reported data and analyze reliability in relationship to medical record data. The research will be conducted in the Department of Family Medicine & Community Health and include all patients that meet eligibility criteria. The data collection and analysis will be conducted by trained clinical coordinators and data analysts within the PI's team that have experience with clinical trials in this context at Penn. The expected duration of active subject participation is less than 30 minutes (likely 5-10 minutes).

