### **5. Statistical Analysis:**

We will summarize data using descriptive statistics to assess recruitment response by age, race/ethnicity, and other key patient demographics (Objective 1). For patients who complete the screening tool and who have pack-year information documented in their medical record (anticipate ~20-30% based on prior work), we will explore the reliability of the screening tool (i.e., survey questions) to predict 20 pack-year eligibility for LCS. We will calculate the positive and negative predictive value, sensitivity, and specificity of the screening tool overall and by race, sex, and age group to assess equity. As exploratory analyses, we will use descriptive statistics and logistic regression to evaluate overall uptake of LCS in patients who complete the screening tool and assess relationships between patient characteristics (e.g., age, sex, race), smoking history, and LCS completion. For Objective 2, we have outlined our statistical analysis (see attached).

The long-term objective of this study is to increase pack-year eligibility at the population level and thus we will include all patients who meet age eligibility for LCS. Additionally, prior studies have indicated that survey response rates using are likely to be <30%, and thus including a large sample of patients will enable us adequate sample to assess reliability of the screening tool overall and within important subgroups (e.g., females and Black adults) where there are concerns regarding LCS uptake inequities.

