6. SAMPLE SIZE

To determine the sample size for the trial, we considered a range of hypothesized response rates from 3% to 12% for the 12 arms representing different combinations of messaging and incentives and based on prior research studies. We hypothesized this range of response rates would be plausible for many of the arms and chose the final sample size based on our ability to distinguish statistically two arms towards the extremes of the range. Figure 1 below shows a plot of the 95% confidence intervals for the range of hypothesized response rates (plotted on both x- and left y-axes). With N=6,000 participants total (500 per arm), we would be able to detect a 5-percentage point difference between two arms if one of the arms had a response rate of 3% to approximately 7%. In comparison, with N=3,600 we would only be able to detect a 5-percentage point difference between two arms if one of the arms had a response rate of 3% or lower. Although larger samples would allow us to detect smaller differences, piloting on a larger sample would decrease the number of participants available for future trials. Balancing this logistical concern with power to detect differences between arms, we chose to include N=6,000 participants in this pilot study.

[figure not shown]

Figure 1: Illustration of 95% confidence interval length for potential response rates between 3% and 12%. Response rates are plotted on both the x- and y-axes. Each panel plots confidence intervals for the total sample size (N) given on the right y-axis.

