c. Protocol Deviations

We do not anticipate any major protocol deviations that could impact analysis, but one that would require adjustments would be if participants receive a different intervention than they are assigned to receive. This unlikely event might happen if there is an error in the programming code within WaytoHealth. Prior to analysis, we will review a subset of 50 randomly selected participants to review the content of all intervention messages received and assess concordance with their assigned study arm. If we identify that more than 5% received an incorrect intervention message, we will review all participants to ensure we have correctly classified them in the right intervention arm. After this, we will conduct subgroup analysis with and without misclassified participants to understand the impact on analysis and report our findings. Any misclassified participants might be excluded primary analysis depending upon subgroup analysis and reported as such.

d. Demographic and Baseline Variables

| Demographics and Baseline Variables | Source |
|---|--------|
| Age at index date | EHR |
| Race | EHR |
| Ethnicity | EHR |
| Sex | EHR |
| Sexual Orientation and Gender Identity | EHR |
| Socioeconomic Status (Based on Census-Tract) | EHR |
| Tobacco Use (Current, Former, Never, Unknown) | EHR |
| Pack-Years (Lifetime Smoking) | EHR |
| Other Smoking Data (E.g., Quit Date, Types) | EHR |

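### Objective 1 aims at population-level reliability and eligibility, but plans only crude figures from the minority expected to reply, with no correction for non-response and no breakdown by tobacco status

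*Protocol*

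**What the plan says.** The protocol describes Objective 1 in two ways. Under Objectives it is a feasibility aim: "Assess feasibility of using patient-directed outreach to complete the simplified eligibility tool". Under Study Design the same objective is to "apply to a larger group of patients to assess population-level reliability and eligibility assessment for LCS".

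The analysis is in Study Procedures, 5. Statistical Analysis. For response: "We will summarize data using descriptive statistics to assess recruitment response by age, race/ethnicity, and other key patient demographics". For accuracy, the plan takes completers who also have pack-years in the record ("anticipate ~20-30% based on prior work") and calculates PPV, NPV, sensitivity and specificity, overall and by race, sex and age group. Survey response rates "are likely to be <30" percent. The protocol's answer to low response is a large sample.

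The target group is all eligible patients, "which we estimate will be approximately 6,125 patients across the study timeline". Key Inclusion Criteria list age and a primary care visit, and do not list smoking. Target Population and Accrual mentions tobacco use, but joins it to age with an or.

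SAP 8.d lists EHR baseline variables that include "Tobacco Use (Current, Former, Never, Unknown"). Neither document names weighting, standardization or a non-response sensitivity analysis for Objective 1. The averaging over sex and race in SAP 9.a serves the Objective 2 arm comparison only.

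**The concern.** A large sample narrows the interval around a respondent figure. It does not move that figure toward the population value. Never-smokers can be contacted under the listed criteria, and a smoking survey may draw replies at different rates from current, former and never smokers. The protocol's Subject Privacy section itself accepts that some patients may see smoking questions as a violation of privacy. The direction of any imbalance is unknown.

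The share of patients flagged by the tool depends directly on the smoking mix of those who reply. Accuracy figures pass through a second selection step, because they also need charted pack-years. The planned breakdowns by race, sex and age would show selection on those variables. They would not show selection on tobacco status, which is closely tied to the outcome, and they leave the overall figures uncorrected. The protocol plans to use the tool to identify patients for later trials and to share it with other health systems, so a respondent figure read as a population figure would be carried forward.

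**Working it through.** The documents give no sample-size or precision calculation for Objective 1, so there is no planned figure to reproduce.

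**1. How many patients the estimates rest on.** Inputs are 6,125 patients (taken here as the number contacted, an assumption), 30% response (the top of the protocol's expectation) and 20-30% with charted pack-years.
- Respondents: 6,125 × 0.30 = 1,837.5, about 1,838.
- Accuracy base: 1,837.5 × 0.20 = 367.5 and 1,837.5 × 0.30 = 551.25, about 368 to 551.
- As a share of those contacted: 0.30 × 0.20 = 6% to 0.30 × 0.30 = 9%.

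**2. Effect on the tool-positive share.** All inputs here are assumptions, because the documents give none by smoking status.

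| | Current | Former | Never |
|---|---|---|---|
| Share of contacted | 12% | 30% | 58% |
| 20+ pack-years | 55% | 35% | 0% |
| Sensitivity | 85% | 85% | 85% |
| Specificity | 80% | 85% | 99% |

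Tool-positive within a stratum = prev × sens + (1 − prev) × (1 − spec):
- Current: 0.55 × 0.85 + 0.45 × 0.20 = 0.5575
- Former: 0.35 × 0.85 + 0.65 × 0.15 = 0.395
- Never: 1 × 0.01 = 0.01

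True share: 0.12 × 0.5575 + 0.30 × 0.395 + 0.58 × 0.01 = 0.1912.

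With unequal response, each stratum share is multiplied by its relative response and the result is divided by the sum. At 3 : 2 : 1, for example, the weights are 0.36, 0.60 and 0.58 (sum 1.54), so the crude share is (0.2007 + 0.2370 + 0.0058) / 1.54 = 0.288. PPV, NPV and specificity come from the same weighted sums of true and false positives and negatives.

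| Relative response (current : former : never) | Tool-positive | PPV | NPV | Specificity |
|---|---|---|---|---|
| Equal (truth) | 19.1% | 76.0% | 96.8% | 94.5% |
| 2 : 1.5 : 1 | 25.0% | 77.5% | 95.4% | 92.7% |
| 3 : 2 : 1 | 28.8% | 78.2% | 94.4% | 91.5% |
| 0.6 : 0.8 : 1 | 15.8% | 74.6% | 97.5% | 95.4% |

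The crude share runs from 0.8 to 1.5 times the truth (15.8 / 19.1 and 28.8 / 19.1). PPV moves at most 2.2 points.

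**3. If only ever-smokers have charted pack-years.** The documents do not say. Using the same inputs for current and former smokers only:

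| Relative response (current : former) | PPV | NPV | Specificity |
|---|---|---|---|
| Equal | 78.4% | 89.1% | 83.9% |
| 2 : 1.5 | 79.0% | 88.5% | 83.7% |
| 3 : 2 | 79.2% | 88.3% | 83.5% |

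Every movement is under 1 point.

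**4. A second set of assumptions.** Suppose 40% of contacted patients are ever-smokers, eligibility is 50% in them and 5% in others, and sensitivity and specificity are both 85% throughout.
- True eligibility: 0.40 × 0.50 + 0.60 × 0.05 = 23.0%.
- Ever-smokers reply twice as often (30% v 15%): (0.06 + 0.0045) / 0.21 = 30.7%.
- Ever-smokers reply half as often (15% v 30%): (0.03 + 0.009) / 0.24 = 16.3%.
- PPV is 62.9% in truth and 52.4% to 71.5% in respondents, if pack-years are charted equally in both strata.

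Weighting each stratum by the inverse of its response rate returns 23.0% exactly, but only because response here is unrelated to pack-years within strata. With equal response there is no bias.

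**The case against.** The strongest reply is that the largest effect falls on a quantity the Statistical Analysis section does not list. That section names response descriptives, four accuracy measures and LCS uptake. Population-level eligibility assessment could mean applying the tool across the population, not estimating a prevalence. Objectives words Objective 1 as feasibility, and the accuracy work is described as exploratory. The tool will be used through outreach, so performance among those who reply is a legitimate target. Outreach is multimodal, and in Spanish where needed. Most of this stands, and it is why narrowing the wording is part of the remedy. It does not remove the mismatch, because Study Design attaches population-level reliability and eligibility to Objective 1 and the analysis has nothing that supports it.

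A reader might infer more than the documents support:
- **That 30% is a ceiling.** It is an expectation.
- **That the SAP's 3% to 12% is the response among all contacted patients.** SAP 6 says "we considered a range of hypothesized response rates from 3% to 12% for the 12 arms". Those arms hold patients who have confirmed their name, and the endpoint closes 7 days after first outreach. The protocol adds later letters, email, portal, post and phone.
- **That EHR covariates are complete for every contacted patient.** Tobacco use has an Unknown level, SAP 7.d allows unknown race, and SAP 8.d lists variables for the randomized trial.
- **That the planned accuracy figures are badly biased.** Steps 2 to 4 of the working show shifts from under 1 point to about 10 points, depending on assumptions the documents cannot settle.
- **That weighting for response would license a population-level accuracy claim.** It would leave selection on pack-year documentation untouched.

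**Conclusion.** The point holds in a limited form. The stated aim is population-level. The planned estimates are crude, come from an expected minority of patients (about 6-9% of 6,125 for accuracy at 30% response), and have neither a non-response correction nor a breakdown by tobacco status. Absence of weighting is read from the silence of both documents.

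The tool-positive share is the figure most exposed. In the main illustration a true 19.1% appears as 15.8% to 28.8%, depending on which group replies more. Those inputs are assumed and the direction is unknown. The effect on PPV, NPV and specificity is smaller or uncertain and turns on whose pack-years are charted. This is an inexpensive improvement to the analysis plan and does not invalidate the study.

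**What to change.** In the protocol's Statistical Analysis section, for Objective 1:
- Beside the crude value, report the tool-positive share weighted by inverse probability of response. Model response among all contacted patients on EHR age, sex, race/ethnicity and tobacco status, with Unknown kept as a level, and give bootstrap confidence intervals.
- For PPV, NPV, sensitivity and specificity, add a sensitivity analysis whose weights model both response and pack-year documentation.
- State that weighting corrects only for measured factors.
- Word conclusions from crude figures as applying to respondents and, for accuracy, to respondents with charted pack-years.
- Fix the contacted denominator first. The protocol gives about 6,125 patients to include, while SAP 7.a waits for at least 6,000 randomized, all of whom must first confirm their name.

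The cost is wider intervals and a little more analysis. No new data collection should be needed, since describing response by demographics already requires EHR data on non-responders and tobacco status is an EHR variable.

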## **METHODS:**

### **1. Study Instruments:**

Participants will be asked to complete three survey questions that have been previously assessed to predict pack-year eligibility of LCS using a yes/no format. We are using a yes/no format because it reduces cognitive burden on survey respondents and therefore believe it is a more equitable approach to assessing pack-years. The survey questions are as follows and all have the same response options (Yes/No):

1. If you add up all the years when you regularly smoked cigarettes, have you smoked for 20 years or more of your life?
2. At any time in your life, did you ever regularly smoke one or more pack(s) of cigarettes per day?
3. Have you ever smoked cigarettes in the last 15 years?

### **2. Group Modifications:**

For patients for which their primary language is listed as Spanish in the EHR, we will translate and send all study information in Spanish.

### **3. Method for Assigning Subjects to Groups: Randomization**

The primary survey questions will not change regardless of study group. However, to enhance response, we will iteratively test how recruitment messages and offering remuneration for completing the survey impacts survey response. Specifically, we intend to randomly assign patients to one of 12 different message groups, half of which will include an incentive for completing the survey. The different groups will have slightly different introductory messaging (see recruitment materials for full messages) and we will compare survey response rates between approaches. During the study, we will review response rates and may adapt assignment to be aligned with the most effective and equitable approaches. This is meant to be exploratory and secondary to the primary aims of the study. See the include statistical analysis plan for updated information on this.

